17.2. Secondary Safety and Reactogenicity

The secondary safety and reactogenicity analyses will be performed for the ES.

17.2.1. Secondary Safety and Reactogenicity Variables & Derivations

The secondary safety and reactogenicity endpoints are:

- Solicited events:
 - Percentage of participants reporting each solicited administration site event within 7 days (Day 1 Day 7) after each vaccine dose
 - Percentage of participants reporting each solicited systemic event within 7 days (Day 1 Day 7) after each vaccine dose
- Unsolicited adverse events:
 - Percentage of participants reporting unsolicited adverse event within 28 days (Day 1 Day 28) after each vaccine dose
- Potential immune-mediated disease (pIMDs)
 - Percentage of participants reporting pIMDs from first vaccination up to study end. A pIMD is an Adverse Event of Special Interest (AESI)
- Pregnancy outcomes
 - Percentage of participants who experienced pregnancy and their outcomes from Day 1 of pregnancy up to study end.

17.2.2. Intercurrent Event Handling and Data Imputation for Secondary Safety and Reactogenicity Variable(s)

See Table A:.

17.2.3. Analysis of Secondary Safety and Reactogenicity Variables

17.2.3.1. SOLICITED EVENTS

For each study group and overall and each solicited event, the incidence rate (frequencies and percentages) of vaccinated participants with solicited administration site events (pain at injection site, redness at injection site and swelling at injection site) and systemic events (fever, headache, myalgia, arthralgia and fatigue) within 7 days after

Document: \\quintiles.net\Enterprise\Apps\sasdata\SAS\\SAS\GlaxoSmithKline\HPV\213749

(HPV9)\Biostatistics\Documentation\SAP\GSK 213749(HPV9-AS04-

001)_WZA97329_SAP_Final_v3.0_02FEB2024.docx

Author: PPD Version Number: 3.0

Version Date: 02FEB2024

Template No.: CS_TP_BS016 Revision 7 Reference: CS_WI_BS005

Page 46 of 48

each vaccine administration will be summarized (any, leading to medical advice) over the whole vaccination course with the exact 95% CI. The completeness defined as the percentage of vaccinated participants who documented presence/absence of each event as well as the daily prevalence of each symptom among vaccinated participants who documented presence /absence of the event on that day will be provided. The percentages will be out of the number of participants who have at least one documented event (either present or absent). The number of solicited events will be summarized at the maximum severity per participant. Each solicited event will be counted once regardless of the number of days the event occurred. The number of solicited events will also be summarized by severity. The percentages will be out of the number of participants in the ES for each period (after first vaccine dose, after second vaccine dose, after third vaccine dose, overall (dose) and overall (participant)) expect the overall dose. The overall dose will be out of the total number of doses in the ES.

The duration of each Grade 3 solicited event (split between solicited administration events and systemic events) will be summarized. The duration of the event is defined as the number of days that a participant had an event, for example if an event occurs on day 2 and 4 but the event did not occur on day 3 (or was not captured in the eDiary) then the duration is considered as 2 days. The duration will be summarized numerically (with n, mean, STD, median, minimum and maximum) and also the frequency (the number of events that had a duration of 1, 2, 3,4, >=5 days).

17.2.3.2. Unsolicited Events

For each study group and overall, the incidence rates (frequencies and percentages) of participants/events with unsolicited AEs (any, related, leading to medical attention), occurring within 28-days (Days 1-28) after each vaccine administration and overall will be summarized by SOC and PT with the exact 95% CI. The number of unsolicited events will also be summarized by severity. The percentages will be out of the number of participants in the ES for each period (after first vaccine dose, after second vaccine dose, after third vaccine dose, overall (dose) and overall (participant)) expect the overall dose. The overall dose will be out of the total number of doses in the ES.

Causality, as indicated by the Investigator is classed as "related" and "not related" to HPV vaccine. A "related" AE is defined as an AE with a relationship to study intervention as "related". If a participant reports the same AE more than once within that SOC/PT, the AE with the worst-case relationship to study intervention will be used in the corresponding relationship summaries for each vaccination group.

Unsolicited events will be coded using MedDRA central coding dictionary, version 26.0 or higher. Unsolicited events will be described using frequency and percentage.

Document: \quintiles.net\Enterprise\Apps\sasdata\SAS\SAS\GlaxoSmithKline\HPV\213749

(HPV9)\Biostatistics\Documentation\SAP\GSK_213749(HPV9-AS04-

001)_WZA97329_SAP_Final_v3.0_02FEB2024.docx

Author: PPD Version Number: 3.0

Version Date: 02FEB2024

Template No.: CS_TP_BS016 Revision 7 Reference: CS_WI_BS005

Page 47 of 48

Unsolicited events will be grouped by SOC and PT and summarized by intervention at time of onset of the event. The summary tables will present the number and percentage of total participants and number of events, by SOC and by PT for each intervention group.

For the summaries of unsolicited events, participants who experience the same AE (in terms of the MedDRA SOC and PT) more than once will only be counted once for that event in the number of participants but all occurrences of the same event will be counted in the number of events.

17.2.3.3. POTENTIAL IMMUNE-MEDIATED DISEASE

For each study group and overall, the incidence rates (frequencies and percentages) of participants/events with pIMDs and pIMDs causally related to study vaccine from first vaccination up to study end will be summarized (any and related) over the whole vaccination course with the exact 95% CI.

17.2.3.4. PREGNANCY

For each study group and overall, the percentage of participants who experienced pregnancy during the entire study and around each vaccination (30 days before and 45 days after each vaccination) will be summarized along with their outcomes.

17.3. Laboratory Parameters

Scheduled clinical safety laboratory parameters will be summarized at each visit by grade (grade 0, 1, 2, 3 and 4) according to Table 13 of the protocol. These include:

- Hematology: hemoglobin, hemoglobin change from baseline, White Blood Cell (WBC) increase, WBC decrease, lymphocyte decrease, neutrophils decrease, eosinophils and platelet decrease
- Chemistry: Blood Urea Nitrogen (BUN), Aspartate Aminotransferase (AST) and Alanine Aminotransferase (ALT)

Box plots of the above summary will be presented for the iSRC analysis.

18. DATA NOT SUMMARIZED OR PRESENTED

The other variables and/or domains not summarized or presented are:

Document: \\quintiles.net\Enterprise\Apps\sasdata\SAS\\SAS\GlaxoSmithKline\HPV\213749

(HPV9)\Biostatistics\Documentation\SAP\GSK_213749(HPV9-AS04-

001)_WZA97329_SAP_Final_v3.0_02FEB2024.docx

Author: PPD Version Number: 3.0

Version Date: 02FEB2024

Template No.: CS_TP_BS016 Revision 7 Reference: CS_WI_BS005

Page 48 of 48

- Physical examination
- Vital signs
- Body temperature

These domains and/or variables will not be summarized or presented, but will be available in the clinical study database, SDTM and/or ADaM datasets. Vital signs and body temperature will be presented in a listing.

Document: \\quintiles.net\Enterprise\Apps\sasdata\SASb\SAS\GlaxoSmithKline\HPV\213749

(HPV9)\Biostatistics\Documentation\SAP\GSK_213749(HPV9-AS04-

001)_WZA97329_SAP_Final_v3.0_02FEB2024.docx

Author: PPD Version Number: 3.0

Version Date: 02FEB2024

Template No.: CS_TP_BS016 Revision 7 Reference: CS_WI_BS005

Page 49 of 48

APPENDIX 1. PROGRAMMING CONVENTIONS FOR OUTPUTS

IQVIA Output Conventions

Outputs will be presented according to the following IQVIA Output Conventions

Document Headers

All TFL is to include the following header:

GSK Vaccines Vaccine: HPV

Study 213749 (HPV9) - DELIVERY DESIGNATION

where delivery designation is the name of the current delivery, e.g., DRY-RUN, FINAL ANALYSIS REPORT, etc

Dates & Times

Depending on data available, dates and times will take the form yyyy-mm-ddThh:mm:ss.

Spelling Format

English US

Presentation of Treatment Groups

For outputs, treatment groups will be represented as follows and in the given order:

Treatment Group	For Tables and Figures	For Listings (include if different to tables)
HPV9High	HPV9 High	HPV9 High

Document: \quintiles.net\Enterprise\Apps\sasdata\SAS\SAS\GlaxoSmithKline\HPV\213749

(HPV9)\Biostatistics\Documentation\SAP\GSK 213749(HPV9-AS04-

001)_WZA97329_SAP_Final_v3.0_02FEB2024.docx

Author: PPD Version Number: 3.0

Version Date: 02FEB2024

Template No.: CS_TP_BS016 Revision 7 Reference: CS_WI_BS005

Effective Date: 01Nov2021

Copyright © 2009, 2010, 2012, 2016, 2018, 2019, 2021 IQVIA. All rights reserved. The contents of this document are confidential and proprietary to IQVIA Holdings Inc. and its subsidiaries. Unauthorized use, disclosure or reproduction is strictly prohibited.

Page 51 of 48

Treatment Group	For Tables and Figures	For Listings (include if different to tables)
HPV9Med	HPV9 Med	HPV9 Medium
HPV9Low	HPV9 Low	HPV Low
Gar9	Gardasil 9	Gardasil 9

Presentation of Visits

For outputs, visits will be represented as follows and in that order:

Long Name (default)	Short Name
Visit 1 (Day 1)	Day 1
Visit 2 (Day 7)	Day 7
Visit 3 (Month 2)	Month 2
Visit 4 (Month 3)	Month 3
Visit 5 (Month 6)	Month 6
Visit 6 (Month 7)	Month 7
Visit 7 (Month 12)	Month 12

Listings

All listings will be ordered by the following (unless otherwise indicated in the template):

- Randomized treatment group (or treatment received if it's a safety output), first by HPV9High then HPV9Med, then HPV9Low and then Gardasil9
- Center-subject ID,
- Date (where applicable),

•

Document: \\quintiles.net\Enterprise\Apps\sasdata\SASb\SAS\GlaxoSmithKline\HPV\213749

(HPV9)\Biostatistics\Documentation\SAP\GSK 213749(HPV9-AS04-

001)_WZA97329_SAP_Final_v3.0_02FEB2024.docx

Author: PPD Version Number: 3.0

Version Date: 02FEB2024

Template No.: CS_TP_BS016 Revision 7 Reference: CS_WI_BS005

Page 52 of 48

DECIMAL PLACES

Decimal places for categorical data

- For percentages one decimal will be displayed
- Differences in percentages and their corresponding confidence limits will be displayed with one more
 decimal than the maximum number used to display the individual percentages, for example the
 difference between two percentages displayed with one decimal will be displayed with two decimals.

Decimal places for Demographic and baseline characteristics will be as follows:

The mean, median, and SD for continuous baseline characteristics (age) will be presented with one decimal.

Serological Summary Statistics

The number of decimals used when displaying geometric mean concentrations (GMC) and their confidence limits is shown in the following table:

GMC value	Number of decimals
<0.1	3
>=0.1 and <10	2
>=10 and <1000	1
>=1000	0

When multiple categories of GMC values are present in the same table, the number of decimals displayed should match that of the smallest category (i.e. the one with the higher number of decimals). For example, if GMC values of <0.1 appear in the same table as values of >=0.1 and <10 3 decimals should be displayed for both.

GMC ratios and their confidence limits will be displayed with 2 decimals regardless of the actual values.

Document: \quintiles.net\Enterprise\Apps\sasdata\SAS\SAS\GlaxoSmithKline\HPV\213749

(HPV9)\Biostatistics\Documentation\SAP\GSK_213749(HPV9-AS04-

001)_WZA97329_SAP_Final_v3.0_02FEB2024.docx

Author: PPD Version Number: 3.0

Version Date: 02FEB2024

Template No.: CS TP BS016 Revision 7 Reference: CS WI BS005

Page 53 of 48

APPENDIX 2. Partial Date Conventions

Imputed dates will NOT be presented in the listings.

When partially completed dates (i.e. with missing day or month) are used in calculations, the following standard rules will be applied:

- A missing day will be replaced by 15
- A missing day and month will be replaced by June 30th.

The following exceptions apply:

- Adverse event start dates with missing day:
 - If the event starts in the same month as the study intervention, the contents of AE.AESTRTPT (the flag indicating if the event occurred before or after vaccination) will be used to complete the date. If 'after vaccination' is selected, the imputed start date will match study dose given during that month. If 'before vaccination' is selected, the imputed date will be one day before the study intervention given during that month.
- Adverse event start dates with missing day and month:
 - If the event starts in the same year as study intervention, the contents of AE.AESTRTPT (the flag indicating if the event occurred before or after vaccination) will be used to complete the date. If 'after vaccination' is selected, the imputed start date will match the study intervention given during that year. If 'before vaccination' is selected, the imputed date will be one day before the) study intervention given during that year.

All other cases of incomplete AE or concomitant medication/vaccination start date will follow the standard rules above.

Algorithm for Prior / Concomitant Medications:

START DATE	STOP DATE	ACTION
Known	Known	If stop date < study med start date, assign as prior If stop date >= study med start date and start date <= study med end date, assign as concomitant

Document: \\quintiles.net\Enterprise\Apps\sasdata\SASb\SAS\GlaxoSmithKline\HPV\213749

(HPV9)\Biostatistics\Documentation\SAP\GSK 213749(HPV9-AS04-

001)_WZA97329_SAP_Final_v3.0_02FEB2024.docx

Author: PPD Version Number: 3.0

> Version Date: 02FEB2024

Template No.: CS_TP_BS016 Revision 7 Reference: CS_WI_BS005

Page 54 of 48

START DATE	STOP DATE	ACTION
	Partial	Impute stop date as latest possible date (i.e. last day of month if day unknown or 31st December if day and month are unknown), then: If stop date < study med start date, assign as prior If stop date >= study med start date and start date <= study med end date, assign as concomitant
	Missing	If stop date is missing could never be assumed a prior medication If start date <= study med end date, assign as concomitant
Partial	Known	Impute start date as earliest possible date (i.e. first day of month if day unknown or 1st January if day and month are unknown), then: If stop date < study med start date, assign as prior If stop date >= study med start date and start date <= study med end date, assign as concomitant
	Partial	Impute start date as earliest possible date (i.e. first day of month if day unknown or 1st January if day and month are unknown) and impute stop date as latest possible date (i.e. last day of month if day unknown or 31st December if day and month are unknown), then: If stop date < study med start date, assign as prior If stop date >= study med start date and start date <= study med end date, assign as concomitant
	Missing	Impute start date as earliest possible date (i.e. first day of month if day unknown or 1st January if day and month are unknown), then: If stop date is missing could never be assumed a prior medication If start date <= study med end date, assign as concomitant
Missing	Known	If stop date < study med start date, assign as prior If stop date >= study med start date, assign as concomitant

Document: \\quintiles.net\Enterprise\Apps\sasdata\SASb\SAS\GlaxoSmithKline\HPV\213749

(HPV9)\Biostatistics\Documentation\SAP\GSK 213749(HPV9-AS04-

001)_WZA97329_SAP_Final_v3.0_02FEB2024.docx

Author: PPD Version Number: 3.0

Version Date: 02FEB2024

Template No.: CS_TP_BS016 Revision 7 Reference: CS_WI_BS005

Page 55 of 48

START DATE	STOP DATE	ACTION
	Partial	Impute stop date as latest possible date (i.e. last day of month if day
		unknown or 31st December if day and month are unknown), then:
		If stop date < study med start date, assign as prior
		If stop date >= study med start date, assign as concomitant
	Missing	Assign as concomitant

Document: \\quintiles.net\Enterprise\Apps\sasdata\SASb\SAS\GlaxoSmithKline\HPV\213749

(HPV9)\Biostatistics\Documentation\SAP\GSK 213749(HPV9-AS04-

001)_WZA97329_SAP_Final_v3.0_02FEB2024.docx

Author: PPD Version Number: 3.0

Version Date: 02FEB2024

Template No.: CS_TP_BS016 Revision 7 Reference: CS_WI_BS005

TABLE, FIGURES AND LISTINGS SHELLS

213749 (HPV9-AS04-001)

A Phase 1/2 randomized, observer-blinded, multi-country study to evaluate safety and immunogenicity of investigational adjuvanted human papillomavirus vaccine in females (16 to 26 years of age)

AUTHOR:

VERSION NUMBER AND DATE: V3.0, 05FEB2024

Document:

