6.8.1. Recording of Concomitant Medications/Products and Concomitant Vaccinations

The following concomitant medication(s)/product(s)/vaccine(s) must be recorded in the eCRF:

- All concomitant medications/products, except vitamins and dietary supplements, administered during the 28-day period following each dose of study vaccine.
- Any concomitant vaccination administered in the period starting from the first dose of study vaccine and ending at the last study visit.
- All concomitant medication associated with AE, including vaccines/products, except vitamins and dietary supplements, administered after the first dose of study intervention.

- All concomitant medication leading to discontinuation of the study intervention or elimination from the analysis, including products/vaccines (refer to Section 5.2.2 and Section 9.3 for further details).
- Prophylactic medication (i.e., medication administered in the absence of ANY symptom and in anticipation of a reaction to the vaccination).
 - For example, an anti-pyretic is considered to be prophylactic when it is given in the absence of fever and any other symptom, to prevent fever from occurring
- Any concomitant medications/products/vaccines relevant to an SAE/potentially immune-mediated response (pIMD) to be reported as per protocol or administered during the study period for the treatment of an SAE/pIMD. In addition, concomitant medications relevant to SAEs and pIMD need to be recorded on the expedited AE report.

The Medical Monitor should be contacted if there are any questions regarding concomitant or prior therapy.

The record of a concomitant medication should include at a minimum the reason for use, dates of administration including start and end dates, dosage information including dose and frequency.

6.8.2. Concomitant Medications/Products/Vaccines That May Lead to Elimination of a Participant From Per Protocol Analyses

The use of the concomitant medications/products/vaccines listed in Section 5.2.2 will not require withdrawal of the participant from the study but may determine a participant's evaluability in the per protocol analysis. See Section 9.3 for cohorts to be analyzed.

6.9. Intercurrent Medical Conditions That May Lead to Elimination of a Participant From Per Protocol Analyses

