14. MEDICATIONS

The percentage of participants who started medications after study vaccination will be presented by intervention group for the ES.

See APPENDIX 2 for handling of partial dates for medications, in the case where it is not possible to define a medication as prior or concomitant, the medication will be classified by the worst case; i.e., concomitant.

- 'Prior' medications are medications which started prior to the dose of study vaccination.
- 'Concomitant' medications are medications which started on or after the day of the administration of study vaccination

Further details are in Section 6.8 of the Protocol. Concomitant medications during the study will be presented in table summaries (Any, any antipyretic, any prophylactic antipyretic, any antibiotic) and in listings for all medications.

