Concomitant vaccinations are any vaccines that the participant received at the time of enrolment or received during the study.

Programming Notes

Output ID: CM0001

[Source: \quintiles.net\Enterprise\Apps\sasdata\SASb\SAS\GlaxoSmithKline\HPV\213749

(HPV9) \Biostatistics\Filename.sas] IQVIA DDMMMYYYY HH:MM

Document: \\quintiles.net\Enterprise\Apps\sasdata\SASb\SAS\GlaxoSmithKline\HPV\213749 (HPV9)\Biostatistics\Documentation\SAP\Shells\

GSK 213749(HPV9-AS04-001)_WZA97329_TFL Shells_V3.0_05FEB2024.docx

Author:

Version Number: 3.0

Version Date: 05FFB2024

Table 14.1.4.4: Summary of Participants starting a Concomitant Medication within 30 days following each dose and overall (Exposed Set)

GSK Vaccines Page X of Y

Study 213749 - DELIVERY DESIGNATION

Period: After first vaccine dose / After second vaccine dose / After third vaccine dose / Overall (dose) / Overall (participant)

		HPV9 High (N=XXX)	HPV9 Medium (N=XXX)	HPV9 Low (N=XXX)	Gardasil 9 (N=XXX)	Total (N=XXX)
Any medications	n (%)	x (x.x)	x (x.x)	x (x.x)	x (x.x)	x (x.x)
	[95% CI]	[xx.x, xx.x]	[xx.x, xx.x]	[xx.x, xx.x]	[xx.x, xx.x]	[xx.x, xx.x]
any antipyretic	n (%)	x (x.x)	x (x.x)	x (x.x)	x (x.x)	x (x.x)
	[95% CI]	[xx.x, xx.x]	[xx.x, xx.x]	[xx.x, xx.x]	[xx.x, xx.x]	[xx.x, xx.x
\n. nranb] actic antinumatic	n (%)	x (x.x)	x (x.x)	x (x.x)	x (x.x)	x (x.x)
Any prophylactic antipyretic	[95% CI]	[xx.x, xx.x]	[xx.x, xx.x]	[xx.x, xx.x]	[xx.x, xx.x]	[xx.x, xx.x
North and Alledon Andrew	n (%)	x (x.x)	x (x.x)	x (x.x)	x (x.x)	x (x.x)
Any antibiotic	[95% CI]	[xx.x, xx.x]	[xx.x, xx.x]	[xx.x, xx.x]	[xx.x, xx.x]	[xx.x, xx.x

Source: Listing xx.x.x.x

Abbreviations: HPV = Human Papillomavirus. CI = Confidence Interval.

N is the number of participants in the Exposed Set for each period except Overall dose, where N is the total number of doses in the Exposed Set.

n is the number of participants with an event in the Exposed Set for each period except Overall dose, where n is the total number of doses in the Exposed Set where an event occurs.

Percentages are calculated as 100 * n/N.

95% CI are based on Clopper-Pearson

[Source: \\quintiles.net\Enterprise\Apps\sasdata\SASb\SAS\GlaxoSmithKline\HPV\213749 (HPV9)\Biostatistics\Filename.sas] IQVIA DDMMMYYYY HH:MM

PPD Version Number: 3.0

Author:

Version Nate: 05FEB2024

Table 14.1.5: Study Vaccine Administration (Exposed Set)

GSK Vaccines Page X of Y

Study 213749 - DELIVERY DESIGNATION

Table 14.1.5 Study Vaccine Exposure Exposed Set

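### SAP Appendix 2 caps a concomitant medication's start at an undefined end date; read as the last dose, most later starts get no class, against SAP Section 14

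*SAP*

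**What the plan says.** SAP Section 14 defines the two classes by start date alone. Prior drugs began before the study vaccination, and concomitant "medications are medications which started on or after the day of the administration of study vaccination". There is no upper limit. The section plans summaries of "Any, any antipyretic, any prophylactic antipyretic, any antibiotic" and a listing of all medications. For partial dates it refers to Appendix 2 and adds that where "it is not possible to define a medication as prior or concomitant, the medication will be classified by the worst case", which it identifies as concomitant.

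The algorithm in SAP Appendix 2 is laid out by whether the start and stop dates are known, partial or missing:

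- Known or partial start, with a known or partial stop (four rows): "If stop date >= study med start date and start date <= study med end date, assign as concomitant".
- Known or partial start, with a missing stop (two rows): "If start date <= study med end date, assign as concomitant".
- Missing start, with a known or partial stop: "If stop date >= study med start date, assign as concomitant", with no limit on the start.
- Both missing: concomitant.

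No row says what to do with a start later than the end date, and *study med end date* is not defined anywhere in the SAP.

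The output shell for Table 14.1.4.4 is titled "Summary of Participants starting a Concomitant Medication within 30 days following each dose and overall (Exposed Set"). It has a separate period for the third dose. The footnote of Listing 16.2.4.4 repeats the Section 14 definition. Protocol Section 6.8.1 requires recording of medications "administered during the 28-day period following each dose of study vaccine", which includes dose 3.

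**The concern.** The two parts of the SAP give different answers for the same drug. Section 14 calls an antipyretic begun the day after dose 3 concomitant. Appendix 2 does not, unless the end date lies well beyond the last dose. If the program follows Appendix 2, the drug carries neither label and drops out of a table restricted to concomitant medications.

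What is at stake is the descriptive account of medication, antipyretic and antibiotic use after the final dose, which sits beside the solicited-event summaries for that dose. Women who stop after dose 1 or dose 2 are affected in the same way after their own last dose.

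There is also a mismatch in the other direction. A drug begun before dose 1 and still being taken is prior under Section 14 and concomitant under Appendix 2.

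**Working it through.** The plan gives no figure to reproduce, so the check is to apply each rule to the same dates.

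**Inputs.** Study medication starts at dose 1. Dose 3 is taken at 180 days, the planned Visit 1 to Visit 5 interval in Protocol Table 2. The table window is 30 days after each dose. The end date is an assumption and is tried two ways: the last dose, and Month 12 (360 days).

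**Rules.** Appendix 2, with a start date present:
- prior if stop < dose 1;
- concomitant if stop ≥ dose 1 and start ≤ end date (with no stop date, only the second condition applies);
- otherwise no class.

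Section 14: concomitant if start ≥ dose 1, otherwise prior.

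| Medication | Appendix 2, end = dose 3 | Section 14 | Appendix 2, end = Month 12 |
|---|---|---|---|
| Starts 20 days before dose 1, stops 5 days before | prior | prior | prior |
| Starts 20 days before dose 1, stops 5 days after | concomitant | prior | concomitant |
| Starts 1 day after dose 1 | concomitant | concomitant | concomitant |
| Starts 1 day after dose 2 | concomitant | concomitant | concomitant |
| Starts on the day of dose 3 | concomitant | concomitant | concomitant |
| Starts 1 day after dose 3 | no class | concomitant | concomitant |
| Starts 10 days after dose 3, ongoing | no class | concomitant | concomitant |
| Starts 29 days after dose 3 | no class | concomitant | concomitant |

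**Count after dose 3.** Let d be the days from dose 3 to the start, d = 0 to 29, which gives 30 possible start days. With the end date at dose 3, start ≤ end requires d ≤ 0. One day qualifies and 30 − 1 = 29 do not. With the end date at Month 12, or with the limit removed, all 30 qualify. These are start days, not medications. The documents give no distribution of start days, so the share of medications lost cannot be computed.

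**Early stoppers.** For a woman who received only dose 1, the end date is dose 1, and a drug begun the next day has no class.

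**What escapes the limit.** A missing start with a stop 5 days after dose 3 is concomitant, because that row has no limit. A partial start is imputed to the earliest possible date. With dose 3 on 9 July 2023, a start recorded only as July 2023 becomes 1 July and is kept. One recorded only as August 2023 becomes 1 August, later than 9 July, and has no class. So some partial dates are rescued and others are not.

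**The case against.** **The end date is undefined, so reading it as the last dose is an inference.** This stands, and the conclusion depends on it. A reader might infer that the term can only mean the last dose; the SAP does not say so. But SAP Section 15 takes exposure from the date and time of each administration, and nothing in the SAP places the end of study medication at Month 12, the alternative that was shown to remove the problem.

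**Section 14's worst-case default would catch these drugs.** It might, but the clause sits in the sentence on partial dates. A drug with complete dates that fails both conditions is not plainly covered.

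**Appendix 2 is only about partial dates, so Section 14 governs.** The appendix title and the cross-reference support this in part. However, the first row of the algorithm deals with two fully known dates, so the limit is stated for complete data as well. The table title and the listing footnote do follow Section 14. That shows what was intended, but it does not remove the conflicting rule.

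**The consequence is small.** This largely stands. Concomitant medication is neither an objective nor an endpoint, and the rule is the same in all four groups. A reader might infer that the comparison of formulations would be biased, or that post-dose-3 medication data would be lost altogether. The documents support neither: the limit does not depend on group, and the listings keep every medication. A near-empty period in all groups might well be noticed as an error.

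**The mismatch for drugs ongoing at dose 1 does not reach Table 14.1.4.4.** Correct. That table counts medications started after a dose, so a drug begun before dose 1 is outside it under either rule. The mismatch bears on the prior or concomitant label in the listing.

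**The 30-day window is not simply wrong.** Also correct. Protocol Section 9.4.3 asks for medication summaries over 30 days for the safety committee, and Section 6.8.1 records AE-associated medication beyond 28 days. A reader might infer that the table must be cut to Days 1 to 28; the protocol does not settle that.

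**Conclusion.** The contradiction is real and should be corrected. All six rows with a known or partial start date carry a limit that Section 14, the Listing 16.2.4.4 footnote and the post-dose-3 period of Table 14.1.4.4 do not allow for. With the end date read as the last dose, 29 of the 30 start days counted from the day of that dose yield no class. What remains is same-day starts, missing start dates and some partial dates imputed to an earlier day. The summary of medication, antipyretic and antibiotic use after the last dose would then be largely empty in every group.

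This rests on two assumptions: the last-dose reading, and the program following Appendix 2 literally. If the end date were Month 12, none of the 30 start days would be lost, but the SAP would have to say so. The effect is confined to a descriptive safety table and a listing label.

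**What to change.** In Appendix 2, delete the upper limit on the start date from the six rows that carry it, including the two with a missing stop date. Alternatively, define *study med end date* so that it covers follow-up after the last dose. Either change brings Appendix 2 into line with Section 14 for drugs begun after the last dose.

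Choose one definition for drugs begun before dose 1 and still being taken, and use it in Section 14, Appendix 2 and the listing footnote.

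As a separate item, reconcile the 30-day window of Table 14.1.4.4 with the 28-day recording period in Protocol Section 6.8.1 and the 30-day summaries in Protocol Section 9.4.3, and state which window the table uses and why.

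The cost is SAP and shell wording and a small change to program logic. No new data are needed.
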